### **Unrelated**

- a. Unlikely : An event with a temporal relationship to drug administration which makes a causal relationship improbable, and in which other drugs, chemicals or underlying disease provide plausible explanations.

### **Intensity of AE**

The intensity of the AE should be judged based on the following:

Mild: Awareness of sign(s) or symptom(s) which is/are easily tolerated

Moderate: Enough discomfort to cause interference with usual activity

Severe: Incapacitating or causing inability to work or to perform usual activities

### **Pregnancy**

In rare cases, pregnancy might occur in a study. Once a subject has been enrolled into the study, after having taken study medication, JARDIANCE DUO® the investigator must report any drug exposure during pregnancy which occurred in a female subject or in a partner to a male subject to the Sponsor's LPVM by means of Part A of the Pregnancy Monitoring Form. The outcome of the pregnancy associated with the drug exposure during pregnancy must be followed up and reported by means of Part B of the Pregnancy Monitoring Form.

In the absence of a reportable AE/AESI, only the Pregnancy Monitoring Form must be completed, otherwise the NIS AE form is to be completed and forwarded as well within the respective timelines.

The ISF will contain the Pregnancy Monitoring Form (Part A and B).

### **Expedited Reporting of AEs and Drug Exposure During Pregnancy**

The following must be reported by the investigator on the NIS AE form from signing the informed consent onwards until the end of the study:

Type of Report	Timeline
All Serious Adverse Events (SAEs), Always Serious Adverse Events (ASAEs) and Adverse	immediately within 24 hours

Event of Special interest	
* 13.2 SAE/ Non-Serious Adverse Reaction Report	
All AEs with fatal outcome * 13.2 SAE/ Non-Serious Adverse Reaction Report	immediately within 24 hours
All non-serious Adverse Reactions associated with JARDIANCE DUO® (empagliflozin/metformin) * 13.2 SAE/ Non-Serious Adverse Reaction Report	7 calendar days
All pregnancy monitoring forms * 13.3 Pregnancy Monitoring Form A, B	7 calendar days

The same timelines apply if follow-up information becomes available for the respective events. In specific occasions the Investigator could inform the Sponsor upfront via telephone. This does not replace the requirement to complete and fax the NIS AE form.

All other Adverse Events must be reported using eCRF within 2 weeks to the Sponsor.

### **Information required**

For each reportable AE, the investigator should provide the information requested on the appropriate (e)CRF pages and the NIS AE form.

For each AE, the investigator will provide the onset, end, intensity, outcome, seriousness and action taken with JARDIANCE DUO® tablets. The investigator will determine the relationship of JARDIANCE DUO® tablets to all AEs as defined in the 'Adverse Event Reporting' section of the physician binder.

### **Reporting of related AEs associated with any other BI drug**

The investigator is encouraged to report all adverse events related to any BI drug other than JARDIANCE DUO® according to the local regulatory requirements for spontaneous AE reporting at the investigator's discretion by using the locally established routes and AE report forms. The term AE includes drug exposure during pregnancy, and, regardless of whether an AE occurred or not, any abuse, off-label use, misuse, medication error, occupational exposure, lack of effect, and unexpected benefit.

## **10.3 REPORTING TO HEALTH AUTHORITIES**

Adverse event reporting to regulatory agencies will be done by the MAH according to local and international regulatory requirements.

## **11. PLANS FOR DISSEMINATING AND COMMUNICATING STUDY RESULTS**

The rights of the investigator and of the sponsor with regard to publication of the results of this study are described in the investigator contract. As a general rule, no study results should be published prior to finalization of the Study Report.

## **13. APPENDICES**

### **13.1 ELECTRONIC CASE REPORT FORM**

Please refer to “ELECTRONIC CASE REPORT FORM” in site file or in electronic CRF web page for the latest version.

## 13.2 SAE/ NON-SERIOUS ADVERSE REACTION REPORT

**Non-Interventional  
Study (NIS) Adverse  
Event Form**

BI Study No: 1276.39

Country:

Site No:

Subject No:

No. of pages, including this page:

To: Boehringer Ingelheim [or CRO] [Address]	From: [site stamp]
[Fax number]	

BY SIGNING THIS FORM, YOU ARE CONFIRMING THAT THE INFORMATION CONTAINED HEREIN IS ACCURATE.

Record all dates in ddmmmyyyy format (e.g. 01Jan2016)

Type of report	Date	Investigator's signature	Remarks
 Initial	_____	_____	_____
 Follow-up	_____	_____	_____
 Follow-up	_____	_____	_____
 Follow-up	_____	_____	_____
 Follow-up	_____	_____	_____
 Follow-up	_____	_____	_____
 Follow-up	_____	_____	_____

## SUBJECT DEMOGRAPHICS

Year of birth: \_\_\_\_\_

Height \_\_\_\_\_ (cm)

Weight \_\_\_\_\_ (kg)

If unknown, record 'UNK'

Sex:  Male   FemalePregnant:  No   Yes weeksIf pregnant, please submit completed Pregnancy Monitoring Form for Studies

**Non-Interventional  
Study (NIS) Adverse  
Event Form**

BI Study No: 1276.39	Country:
Site No:	Subject No:

**EVENT INFORMATION**

Record all dates in ddmmmyyyy format (e.g. 01Jan2016). If ongoing, enter 'CONT.' Record all times in 24-hour (hh:mm) format. If time is unknown, record 'UNK.'

	Event No. [ ]	Event No. [ ]	Event No. [ ]	Event No. [ ]				
Adverse Event term (if available, enter the diagnosis)								
Onset date								
Onset time								
End date								
End time								
Was the event serious?	 Yes	 No	 Yes	 No	 Yes	 No	 Yes	 No
If serious, please mark reason for seriousness	 Results in death							
	 Immediately life-threatening							
	 Persistent or significant disability/incapacity							
	 Requires/prolongs hospitalisation							
	 Congenital anomaly/birth defect							
	 Other comparable medical criteria (specify in Description of Event section)							
Was the event a protocol-specified Adverse Event of Special Interest (AESI)?	 Yes	 No	 Yes	 No	 Yes	 No	 Yes	 No
Is there a reasonable causal relationship between the Adverse Event and: (provide description of rationale, other possible causes on page 3)								
BI studied medication or BI product given for the disease in scope of NIS	 Yes	 No	 Yes	 No	 Yes	 No	 Yes	 No
Concomitant medications: Please refer to concomitant medication section to document causal relationship.								
Outcome of event (check only one)								
Recovered (report AE end date above)								
Not yet recovered								
Recovered with sequelae (report AE end date above)								
Unknown								
Fatal								
If fatal, was this event the primary cause of death?	 Yes	 No	 Yes	 No	 Yes	 No	 Yes	 No
If subject died, record date of death:								
Was an autopsy performed?	 Yes		 No		 Unknown			
Was therapy for the event administered?	 Yes	 No	 Yes	 No	 Yes	 No	 Yes	 No
If yes, specify therapy in Description of Event section.								
Was a dechallenge performed?	 Yes	 No	 NA	 Yes	 No	 NA	 Yes	 No
If yes, did the event disappear or significantly decrease in intensity after the BI product was stopped?	 Yes	 No		 Yes	 No		 Yes	 No
Was a rechallenge performed?	 Yes	 No	 NA	 Yes	 No	 NA	 Yes	 No
If yes, did the event reappear after reintroduction?	 Yes	 No		 Yes	 No		 Yes	 No

**Non-Interventional  
Study (NIS) Adverse  
Event Form**

BI Study No: 1276.39	Country:
Site No:	Subject No:

**RATIONALE FOR CAUSALITY ASSESSMENT**

*Please document the event(s) and provide your rationale for the causal assessment to BI product and include a rationale for any other causal relationships which are considered relevant. Rationale may include temporal relationships, confounding factors (i.e. disease/medication), positive dechallenge/rechallenge, interactions with other medications and/or pattern of reaction.*

**DESCRIPTION OF THE EVENT(S)**

*Please highlight any additional information (not otherwise provided on this form) which may contribute to the assessment of the case including but not limited to: relevant diagnostic/lab test results (with reference ranges) and therapeutic measures given for event.*

**Non-Interventional  
Study (NIS) Adverse  
Event Form**

BI Study No: 1276.39

Country:

Site No:

Subject No:

## RELEVANT BASELINE CONDITIONS INCLUDING PAST MEDICAL HISTORY

Record all dates in ddmmmyyyy format (e.g. 01Jan 2015). If ongoing, enter 'CONT.'

 None	If concomitant, provide onset date	Past - Please check box only if ended prior to (S)AE onset
 Yes (specify below)		
1.		
2.		
3.		
4.		
5.		
6.		

## BOEHRINGER-INGELHEIM PRODUCT

## Indication

Name of BI studied medication or BI product given for the disease in scope of NIS :		
Formulation		
Total daily dose at onset of event (dose, unit)		
Route		
Start date		
Start time		
Date of last administration prior to event		
End date		
End time		
Was the administration correct?	 Yes  No	
If the administration was not correct, check all applicable boxes: overdose, abuse, misuse, medication error, other (i.e. occupational exposure, lack of effect, unexpected benefit)		
 Misuse / Abuse  Medication error  Overdose  Other:		
Action taken with BI studied medication or BI product administered for the disease in scope of NIS as a result of the event (check one)	Dose not changed	
	Dose reduced	
	Dose increased	
	Drug withdrawn	

**Non-Interventional  
Study (NIS) Adverse  
Event Form**

BI Study No: 1276.39	Country:
Site No:	Subject No:

## RELEVANT PAST AND CONCOMITANT MEDICATIONS

Please preferably provide trade name. Do not include medications used solely to treat the adverse event(s).

 None  Yes (specify below)	Indication	Past	Start/end dates ddmmmyyyy or cont.	Total daily dose at onset of event (dose/ unit)	Route	Is there a reasonable causal relationship between the event and the past or concomitant therapy? If Yes, record event number from page 2
1.			Start:			 No  Yes
			End:			
2.			Start:			 No  Yes
			End:			
3.			Start:			 No  Yes
			End:			
4.			Start:			 No  Yes
			End:			
5.			Start:			 No  Yes
			End:			
6.			Start:			 No  Yes
			End:			
7.			Start:			 No  Yes
			End:			
8.			Start:			 No  Yes
			End:			

**13.3 PREGNANCY MONITORING FORM**

Please refer to “PREGNANCY MONITORING FORM” in site file or in electronic CRF web page for the latest version.

**13.4 JARDIANCE DUO® PRESCRIPTION INFORMATION FOR KOREA**

Please refer to “JARDIANCE DUO® Prescription Information for Korea” in site file or in electronic CRF web page for the latest version.

## 14. AMENDMENTS AND UPDATES

Number	Date	Section of study protocol	Amendment or update	Reason
1	25 Apr 2018	8.2.3.2 Visit 1; Baseline Visit 8.2.3.3 Visit 2 8.2.3.4 Visit 3 10.1 Definitions of adverse events 13.Appendices	8.2.3.2 Change of data collection period 8.2.3.3, 8.2.3.4 Addition of Renal function test on Follow up visit 10.1 Addition of 'Always Serious Adverse Events' 10.1 Addition of 'AESI' case (Lower limb amputation)	- Period adjustment for completeness of data collection - Follow up for renal function - Addition of AE collection and method classification method according to BI PV process - Attached appendix separately
2	31 Jan 2019	8.2.2 Study population	8.2.2.1 Add-on therapy to 'linagliptin'	- Updates indication according to approved local label

2.1 Study Objective

Primary Objective

The primary objective of this study is to monitor the safety profile of JARDIANCE DUO in Korean patient with type 2 diabetes mellitus (T2DM) in a routine clinical setting.

Secondary Objective

The secondary objective of this study is to monitor the effectiveness of JARDIANCE DUO by evaluation of the change from baseline after 12 weeks and/or 24 weeks in the glycosylated hemoglobin (HbA1c), [REDACTED]

[REDACTED] in Korean T2DM patients.

2.2 Number of Subjects

The sample size of 600 patients is based on the requirement of the local regulatory authority (MFDS). As per regulation, long-term surveillance is necessary for the T2DM indication. Since T2DM is chronic disease it might be restrictive to collect safety and effectiveness data in short-term (12weeks) period, all patients will be enrolled for long-term (24weeks) surveillance.

2.3 Study Period

Minister of Food and Drug Safety (MFDS) set JARDIANCE DUO re-examination period from 21 January 2016 to 11 August 2020. The study period is granted as the remaining period of JARDIANCE (empagliflozin) according to the Standards for Re-examination of New Drugs.

2.4 Study Method

This study will be carried out in the manner of successive survey that the investigator will be asked to successively write in the case report forms (CRFs) from the subject who was initially administered the drug following the study start date to the requested number of subjects without omission.

3. Sequence of Planned Analyses

In the ‘Guidelines for Re-examination of New Drugs, etc.’, study reporting period is defined as follows (section 1 of Chapter 4).

B. Periodic reports are submitted to the Minister of Food and Drug Safety (MFDS) with results of use-result surveillance and special surveillance that are conducted for 6 months in first 2 years from the license date and for 1 year thereafter within 2 months after the expiration of surveillance period and the final periodic report may be replaced with the re-examination application.

In accordance with the above local regulation, interim analysis will be carried out at the time of the 5th, re-examination of review reporting. However, statistical analysis may not proceed if;

- When the brief report is prepared as a reason for not being executed due to lack of number of cases of reporting;
- If a regular report is prepared as a case study report due to a small number of subjects;

4. Analysis Sets

In this study, the analysis sets for statistical analysis consist of the safety analysis set (section 4.1), the effectiveness analysis set (section 4.2), and the long-term safety analysis set (section 4.3).

4.1 Safety Analysis Set

In the ‘Guidelines for Re-examination of New Drugs, etc.’, study subject is defined as follows (section 3 of Chapter 3).

2) Patient group to be study subjects

A) Patients who have decided to receive the investigational product based on the medical judgment of the investigator are included in the subjects.

B) In principle, those who fall under off-label use of the drug are not included in the subjects. However, if the data of off-label use subjects are collected, they are analyzed as a separate item.

C) The actual method of selecting study subjects should be described in detail.

In this study, the safety analysis set is defined as follows.

The safety analysis set consists of subjects who signed the informed consent form to participate in this study, took the drug at least once, and then received follow-up at least once by the study investigator.

4.2 Effectiveness Analysis Set

In the ‘Guidelines for Re-examination of New Drugs, etc.’, the effectiveness analysis set is defined as follows (section 3 of Chapter 3).

(1) Composition of study subjects

Effectiveness analysis set: Among subjects in the safety analysis set, subjects whose effectiveness evaluation records are collected as specified in the protocol.

In this study, the effectiveness analysis set is defined as follows.

The effectiveness analysis set consists of subjects who received effectiveness evaluation among those in the safety analysis set.

5. General Specifications for Statistical Analyses

5.1 Analysis Software

Each statistical analysis will be carried out with SAS Software version 9.4 or more recent version.

5.2 Planned Covariate

No covariate analysis is planned for this study.

5.3 Summary Statistics

For continuous data, the number of subjects, mean, standard deviation, median, minimum, and maximum are presented, and for categorical data, the frequency and percentage (%) are presented.

5.4 Methods for Missing Data and Incomplete Data

If missing or incomplete data exists, they are processed as follows. However, if separate processing for missing data is required depending on the analysis item, the information will be described in the relevant item of '7.1 Derivation'.

- If there are missing data other than those related to this drug, the collected data will be analyzed as they are without any replacement.
- Among the continuous data used for analysis, data containing inequality signs and symbols (Ex: 'over 20', '>20') are excluded from the analysis.
- If only some information (Ex: '2017-03-UK', '20UK') of the date used in the analysis (Ex: total administration period) exists, and the other part cannot be calculated, it is excluded from the analysis.

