### 8.2.1 Study sites

A total of 600 patients will be enrolled at approximately 20 sites by as many as 20 or more NIS physicians. To minimize the selection bias at the site level, the goal is to have participating centers reflect a balance between general hospitals and clinics for surveillance. The treating physicians will mainly be internists. To minimize the selection bias, consecutive patients from each site who meet inclusion criteria will be enrolled in this study.

As provided in the 『Standards for Re-examination of New Drugs』 of the Ministry of Food and Drug Safety Notification, BI OPU should select study site according to the following requirements;

- ① Equipment/facility, and manpower capable of fully achieving the goal of investigation should be held;
- ② The investigator should have specialized knowledge of the drug subject to investigation and the indication, have completed education/training necessary for performing the investigation, or have practical experience;
- ③ Study site and the investigator should strictly keep confidential the record of subject's personal data
- ④ The investigator should be fully aware of the 『Standards for Re-examination of New Drugs』 and study protocol.

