#### 8.2.2.3 Exclusion criteria:

- Patients with previous exposure to JARDIANCE DUO®
- Hypersensitivity to active ingredients empagliflozin and/or metformin or to any of the excipients
- Moderate (stage 3b) and severe renal failure ( $\text{CrCl} < 45 \text{ ml/min}$  or  $\text{eGFR} < 45 \text{ ml/min/1.73m}^2$ )
- Acute conditions with the potential to alter renal function such as: dehydration, severe infection, cardiovascular collapse (shock), acute myocardial infarction, sepsis
- Type 1 diabetes, acute or chronic metabolic acidosis, including diabetic ketoacidosis with or without coma, history of a ketoacidosis (type 1 diabetes and diabetic ketoacidosis should be treated with insulin).
- Congestive heart failure requiring pharmacologic management, in particular those with unstable or acute congestive heart failure
- Radiologic studies involving the use of intravascular iodinated contrast materials (for example, intravenous urogram, intravenous cholangiography, angiography, and computed tomography (CT) scans with intravascular contrast materials) -  
Intravascular administration of iodinated contrast media may lead to acute renal failure and has been associated with lactic acidosis in patients receiving metformin. Therefore, in patients with  $\text{eGFR} > 60 \text{ ml/min/1.73m}^2$ , JARDIANCE DUO® must be

discontinued prior to, or at the time of the test and not be reinstated until 48 hours afterwards, and only after renal function has been re-evaluated and has not deteriorated further. In patients with moderate renal impairment (eGFR 45-60 ml/min/1.73m^2), JARDIANCE DUO® must be discontinued 48 hours before administration of iodinated contrast media and not be reinstated until at least 48 hours afterwards, and only after renal function has been re-evaluated and has not deteriorated further.

- In patients with severe infections or severe traumatic systemic disorders, JARDIANCE DUO® should be temporarily suspended, and should not be restarted until the patient's oral intake has resumed and renal function has been evaluated as normal.
- JARDIANCE DUO® should be temporarily suspended for any surgical procedure (except minor procedures not associated with restricted intake of food and fluids) before 48 hours, and not be reinstated until 48 hours afterwards, after renal function has been evaluated as normal.
- Patients with malnutrition, starvation, hypostheniam pituitary or adrenal insufficiency

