#### 8.2.3.2 Visit 1; Baseline Visit

Upon patient enrolment, the following will be recorded on the patient's eCRF.

- Information on the site (Hospital name, Department, Physician name, Contract date)
- Visit date
- Diagnosis: date of the diagnosis of T2DM, Family history of T2DM
- Inclusion / Exclusion criteria
- Informed consent form: Date of Informed consent
- Demographic data: Age, gender, pregnancy, height, smoking status
- Diabetes mellitus related complication (Retinopathy, Neuropathy, Nephropathy, Vasculopathy, etc.)
- Medical history: Hypertension, Dislipidemia, Coronary artery disease, Stroke, Liver disease, Renal failure, Allergy, Nephropathy, etc. (history of concomitant disease within 6 months)
- Physical examination: body weight, blood pressure in sitting position (SBP, DBP)
- Renal Function: record Serum creatinine, eGFR, urin ACR if blood test result is available (the most recent data prior to baseline)
- Effectiveness endpoints: HbA1c, [REDACTED] (Lab data should be collected within 1 month prior to baseline)
- Concomitant anti-hyperglycemic agent : record any anti-hyperglycemic agents have been taken prior to the baseline visit (within 1 month prior to baseline)
- Concomitant medications: record all medications have been taken at least once since one month prior to the baseline visit.
- Dose of JARDIANCE DUO® given(Daily dose(Dosage/Administration), Start date)

At visit 1, the patient will be requested to contact the treating physician in the event of any adverse events noted after initiating JARDIANCE DUO® treatment.

#### 8.2.3.3 Visit 2; 12 weeks from Visit 1

After 12 weeks from Visit 1, the patients will return for follow-up. The followings will be noted and recorded in the eCRF.

- Visit date
- Physical examination: body weight, blood pressure in sitting position (SBP, DBP)

Proprietary confidential information © 2019 Boehringer Ingelheim International GmbH or one or more of its affiliated companies

- Any change of JARDIANCE DUO® given (Daily dose(Dosage/Administration), Start date, Date of discontinuation or continuation, Action taken, Causality)
- Effectiveness endpoints: HbA1c, [REDACTED]
- Renal Function: record Serum creatinine, eGFR, urine ACR if blood test result is available (The most recent data since last visit, except previously entered data)
- Concomitant anti-hyperglycemic agent including new medications taken since last visit : any change in the concomitant medications (dose and dosing intervals)

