6.8.5 Other Safety Analyses

When reporting for re-examination, the following items will be categorized based on the incidence (%) by PT (Preferred Term), and information on SOC (System Organ Classes) and PT (Preferred Term) will be presented in a table.

[figure not shown]
- Serious adverse events, Serious adverse drug reactions
- Unexpected adverse events, Unexpected adverse drug reactions

[figure not shown]
At the time of reporting for re-examination, descriptive statistics of serum creatinine, glomerular filtration rate, and albumin-creatinine-ratio measured before administration of this drug and at the final visit are presented. In order to analyze whether there is a difference at the final visit compared to before administration of this drug, the paired t-test is used.

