7.1 Derivation

The items that need to be calculated in this study are as follows, but the following matters may be considered.

- If an additional calculated variable related to the variables defined below is required during statistical analysis, SAP may not be revised, but the variable will be specified in TLFs.
- Depending on the data actually collected, the item units defined in SAP may change (Ex. duration of disease: months → years)

Age

- If the birthday has passed from the date of signing the consent form: (Year of signing the consent form – Year of birth)
- If the birthday has not passed since the date of signing the consent form: (Year of signing consent – Year of birth – 1)

Duration of disease (days)

- (Start date of initial dose of this drug – Date of diagnosis + 1)
- For continuous analysis, if the date is not complete, it is excluded from the analysis.
- For categorical analysis, if the diagnosis date is partially collected, it is analyzed according to the following rules.
 - If 'day' of the diagnosis date is missing: (Year & month of the start date of initial dose of this drug – Year & month of diagnosis date)
 - If there is only 'year' in the diagnosis date: (Year of the start date of initial dose of this drug – Year of the diagnosis date)

Total administration period of this drug (days)

- $\sum_{i=1}^n [(End\ date\ of\ drug)_i - (Start\ date\ of\ drug)_i + 1]$,
i: The i^{th} administration period of the subject in the n times of administration period of this drug
- If the end date of the i^{th} dose is "in progress" or is missing, other than the end date of the last dose:
 - [(one day before start date of $i+1^{th}$ dose) – (dose start date) + 1]
- If the end date of the last dose is 'in progress' or missing, it is substituted in the following order.
 - [(Date of Last visit) – (Start date of drug) + 1]
 - [(Start date of drug) – (Start date of drug) + 1]

Total dose of this drug (empagliflozin/metformin)(mg)

- $\sum_{i=1}^n [(End\ date\ of\ drug)_i - (Start\ date\ of\ drug)_i + 1] * Daily\ dose$
i: The i^{th} administration dose of the subject in the n times of administration dose of this drug

Average of daily dose drug (empagliflozin/metformin)(mg/day)

- Total dose(mg) / Total administration period (days)

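### SAP 5.4 discards values recorded with an inequality sign and SAP 7.1 has no laboratory exception, so an eGFR such as '>90' or an ACR below a limit loses its pair in the SAP 6.8.5 renal comparison

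*SAP*

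**What the plan says.** Among continuous data used for analysis, SAP 5.4 says that "data containing inequality signs and symbols (Ex: 'over 20', '>20') are excluded from the analysis". The same section allows no replacement for other missing data and sends item-specific handling to SAP 7.1.

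SAP 7.1 opens with "The items that need to be calculated in this study are as follows" and then covers age, duration of disease, administration period, total dose and average daily dose. No laboratory variable appears. It lets further calculated variables be added in the TLFs, but only if they relate to the variables defined there.

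SAP 6.8.5 says that "descriptive statistics of serum creatinine, glomerular filtration rate, and albumin-creatinine-ratio measured before administration of this drug and at the final visit are presented", and tests the difference with a paired t-test. SAP 5.3 adds "For continuous data, the number of subjects, mean, standard deviation, median, minimum, and maximum are presented".

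On collection, Protocol 8.2.3.2 says "record Serum creatinine, eGFR, urin ACR if blood test result is available (the most recent data prior to baseline"). Visits 2 and 3 carry a similar if-available instruction. The baseline visit also records "Demographic data: Age, gender, pregnancy, height, smoking status". Protocol 8.2.2.3 excludes "Moderate (stage 3b) and severe renal failure", defined as creatinine clearance or eGFR below 45. Protocol 8.7.5 intends every available value to be used.

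**The concern.** A result of '>90' is not missing: it is known to lie above 90. Under SAP 5.4 it is treated as if nothing were known. At a site whose laboratory reports this way, the patients removed are those with high eGFR, or with low ACR where the limit is a lower one. The eGFR table would then describe patients with poorer renal function than those treated, on fewer pairs.

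A reader of the table could not see this. Renal tests are recorded only if available, so a low n could mean tests not done or tests done and discarded. Safety is the primary objective, and Protocol Amendment 1 added the follow-up renal tests specifically to follow renal function.

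**Working it through.** **Text check.**
1. SAP 5.4 applies to all continuous data used for analysis, so it reaches eGFR, ACR and creatinine.
2. The only place for an exception is SAP 7.1, which has none for laboratory data.
3. A paired t-test needs both values. One signed value, pre-drug or at the final visit, therefore removes the pair for that variable. A signed Visit 2 value does not matter when Visit 3 is the final visit.
4. Creatinine is recorded beside eGFR at all three visits if available, with age and gender at baseline. A numeric eGFR can therefore be calculated wherever a numeric creatinine exists. ACR cannot be recovered from creatinine.

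**Size for eGFR.** The plan gives no figure to reproduce: no eGFR distribution, no reporting limit and no frequency of signed values. From the documents come only the eligibility floor of 45 and the upper bound on pairs ("A total of 600 patients will be enrolled at approximately 20 sites"). Everything else is assumed:
- eGFR mean 88 and total SD 18, with within-person SD 5.66 per measurement (SD of change √2 × 5.66 = 8.0)
- uniform fall of 3.0
- limit '>90'
- all 600 patients with both tests
- a share f of patients at sites that report with the limit.

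Pairs were simulated with observed baseline of at least 45. A pair is dropped if the patient is at such a site and either value exceeds 90. Half-width is 1.96 × SD/√n, and t is the absolute mean change divided by SD/√n.

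| f | Pairs kept (of 600) | Pre-drug mean, kept pairs | Mean change | 95% half-width | t |
|---|---|---|---|---|---|
| 0 | 100% (600) | 88.4 | -3.04 | 1.96 × 7.99/√600 = 0.64 | 9.3 |
| 25% | 87% (525) | 86.4 | -2.98 | 1.96 × 7.91/√525 = 0.68 | 8.6 |
| 50% | 75% (449) | 83.8 | -2.91 | 1.96 × 7.81/√449 = 0.72 | 7.9 |
| 100% | 50% (299) | 74.6 | -2.65 to -2.67 | 1.96 × 7.42/√299 = 0.84 | 6.2 |

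The ranges in the last row are repeat simulation runs. The mean change shifts by 0.06, 0.13 and at most 0.39. The pre-drug mean shifts by 2.0, 4.6 and 13.8.

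**Substituting the limit is worse.** Setting '>90' to 90 gives mean changes of -2.72, -2.40 and -1.76 at f = 25%, 50% and 100%, further from -3.04 than exclusion in each case.

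**What calculated eGFR recovers.** At f = 100%, 301 pairs are lost. If a numeric creatinine pair exists for 80% of those patients, 299 + 0.80 × 301 = 540 pairs are available; for 95%, 585; for all, 600.

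**Size for ACR.** Assumed: log-normal with median 12 and log-SD 1.4, mean log change -0.2 (SD 0.6), limit '<5'. Exclusion keeps 91%, 82% and 64% of pairs at f = 25%, 50% and 100%. The pre-drug median of the kept pairs is 14.0, 16.4 and 23.0 instead of 12. At f = 100%, 27% of pre-drug and 33% of final values fall below 5. Both are under half, so the full-sample medians (12.0 and 9.8) are recovered once those values are kept as below limit.

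**The case against.** The premise is not documented. No section says that any site reports signed renal values, and Protocol 8.8 describes range checks on numeric entries without saying whether a sign is accepted. This stands, and it makes the point conditional. Against it, SAP 5.4 itself anticipates such entries.

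The effect on the mean change is small. At 25% or 50% of patients the shift is 0.06 or 0.13, well inside the half-width of 0.64, and significance is unchanged even at 100%. This stands. The main distortion is in whom the table describes.

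The information is largely covered elsewhere. SAP 6.8.5 makes the same comparison on serum creatinine, and the decreased-renal-function AESI is defined on creatinine. This stands for eGFR but does nothing for ACR.

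The rule is prespecified and beats replacing '>90' by 90. That is true, but a better alternative uses data already collected.

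Two stronger readings are tempting. A reader might infer that the rule removes high eGFR values across the study. It does not: it acts on how a value is recorded, and a site that reports numbers keeps the same high values. A reader might also infer that a lower limit such as '>60' could manufacture a fall in eGFR. The documents give no such limit. In simulation with no true change, the apparent fall of 1.0 to 1.4 depends on the modelled floor at 45 (0.04 to 0.07 without it) and is smaller than its own 95% half-width of 1.8 to 4.0.

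**Conclusion.** The point holds as a conditional weakness in how two renal tables are built. By the text, a signed pre-drug or final-visit eGFR or ACR loses its pair, selectively at sites that report with limits and without a trace in the reported n. How far this matters depends on a frequency that the documents do not give; with no signed values the effect is nil. On the assumed '>90' inputs, 87% to 50% of eGFR pairs remain and the pre-drug mean drops by 2 to 14 units, while the mean change and the t-test conclusion barely move.

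A reader might infer that the study's safety conclusions are at risk. The documents do not support that: AE incidence, the creatinine-based AESI and the creatinine comparison are largely independent of the rule. This is an improvement worth making because it is cheap, not a threat to the primary objective.

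**What to change.** 1. Add an entry to SAP 7.1: for 6.8.5, calculate eGFR for all patients from recorded serum creatinine, age and gender with one prespecified formula, and list site-reported eGFR alongside. Use calculated values throughout rather than mixing the two sources. Do not replace '>90' by 90 as the main analysis.
2. Report the number of signed values by variable and visit, separately from tests not done. This alone shows whether the problem exists.
3. Exempt ACR from the SAP 5.4 exclusion: keep signed values as below limit, and report before and after medians where fewer than half the values are below the limit. No further ACR modelling is needed.

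The cost is one SAP 7.1 entry, one exception in SAP 5.4 and one count table, with no new data. Calculated eGFR may differ slightly from the site-reported value. Patients without a numeric creatinine at both times remain missing. The ACR median is unusable if half or more of the values are below the limit.
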